3.0 Study Hypotheses

3.1 Study hypotheses for specific aim #1 (primary aim):

- Doxycycline is more effective than placebo in the initial management of ESI-related bleeding.
- **Statistically significant difference between the placebo and Doxycycline groups will be shown in favor of Doxycycline**

3.2 Study hypotheses for specific Aim #2 (secondary aim):

- Patients in the Doxycycline group will report a higher satisfaction rate with ESI scores on a survey as compared to those in the placebo arm at 13 weeks post-randomization.
- **Statistically significant difference in patient satisfaction rates between the placebo and Doxycycline groups will be shown in favor of Doxycycline.**

3.3 Study hypotheses for specific aim #3 (secondary aim):

- In patients who request secondary treatment for unacceptable bleeding, administration of Doxycycline will result in a high method continuation rate and patient satisfaction rate at 39 weeks post ESI insertion.
- The above will be supported by method continuation rate of >75% [3, 8] at 26 weeks post-randomization.

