2.0 Specific Aims

2.1 Specific Aim #1 (primary aim):

- To determine the effect of Doxycycline vs. placebo on the need for additional treatment for unacceptable bleeding at 13 weeks post-randomized treatment.

2.2 Specific Aim #2 (secondary aim):

- To determine if initial treatment with Doxycycline results in higher patient satisfaction with ESI as compared to placebo at 13 weeks post-randomized treatment.

2.3 Specific Aim #3 (secondary aim):

- To determine method continuation and patient satisfaction rate at 26 week post-randomization in patients who choose secondary treatment with Doxycycline for unacceptable bleeding at 13 weeks post-randomized treatment.

In order to evaluate specific aim #1:

- All ESI patients will be offered enrollment in the study at ESI insertion and will begin prospective diaries. They will be contacted at 13 weeks post insertion. If patients report unacceptable bleeding at that time or self-report at any time following an initial 13 week interval, they will be offered randomization to Doxycycline or placebo. Patients will continue a weekly prospective symptom diary for the duration of study.
- Time to recurrence of unacceptable bleeding post-treatment and need for secondary treatment (primary endpoint) will be determined by completion of prospective symptom recording by 13 weeks post-randomized treatment.

- Side-effects and adverse events associated with medical treatment will be documented.

In order to evaluate specific aim #2:

- A patient satisfaction survey will be administered at randomization and 13 weeks post-randomization. The results will be compared between the Doxycycline and placebo study arms.

In order to evaluate specific aim #3:

- Patient satisfaction will be assessed at 13 weeks post-ESI insertion.
- Patients who report unacceptable bleeding after initial randomized treatment and who choose additional treatment will receive secondary treatment with Doxycycline and the method continuation rate and patient satisfaction rate at 26 weeks post randomization will be calculated.
- In patients who leave the study prior to 26 weeks post-randomization, patient satisfaction will be recorded at that time.
- If ESI is removed prior to 26 weeks post-enrollment, the reason, date of removal and alternative contraception will be documented.

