5.3.2 Outcome measurements

A. Primary treatment efficacy and safety end point (primary endpoint addressing specific aim #1)

- The efficacy of Doxycycline on ESI-related bleeding will be compared to placebo based on rates of **unacceptable bleeding** and weekly prospective symptom diary at 13 weeks post-randomization.

B. Primary treatment efficacy and safety endpoints (secondary endpoints addressing specific aim #1)

- Method continuation rate at 13 weeks post-randomization will be compared for women in the Doxycycline vs. placebo group.
- Bleeding patterns will be quantified based on the PBLAC and WHO classification of clinically important bleeding patterns over each 13 week reference period.[13,14, 29].
- Incidence of additional symptoms including acne, headache, mood changes in the treatment groups will be compared to placebo at randomization and 13 weeks post-randomization based on the weekly prospective symptom diary
- Interval to recurrence of unacceptable bleeding post-randomized treatment (i.e., need for additional treatment) will be determined
- Rate of adverse events associated with medical treatment will be documented by prospective symptom diary and BMI calculation. These include headache, mood changes, acne and change in BMI.

C. Patient satisfaction with primary treatment endpoint (primary endpoint addressing specific aim #2)

- Patient satisfaction with ESI at randomization for a baseline pre-treatment satisfaction and at 13 weeks post-randomized treatment following primary treatment with Doxycycline vs. placebo will be compared

D. Patient satisfaction with secondary treatment endpoint (primary endpoint addressing specific aim #2)

- Patient satisfaction with ESI at 26 weeks post-randomized treatment for patients with continued unacceptable bleeding following primary treatment who receive secondary treatment with Doxycycline will be calculated.

E. Secondary treatment efficacy and safety endpoint (primary endpoint addressing specific aim #3)

- Method continuation rate at 26 weeks post-randomized treatment for patients with continued unacceptable bleeding after primary treatment who undergo secondary treatment with Doxycycline will be calculated

F. Secondary treatment efficacy and safety endpoint (secondary endpoints addressing specific aim #3)

- Rate of ESI removal for bleeding between 13 and 26 weeks post randomization.

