5.4.1 Power statements

Based on prior Mayo data, we anticipate about 30% of patients will develop unacceptable bleeding following ESI insertion.[3,29] These patients will be approached for participation in this study. The study plans to randomize a total of 100 patients with unacceptable bleeding to either placebo (N=50) or Doxycycline (N=50). The following calculations were based on a two-sided chi-square test with a type I error rate of 0.05.

Aim 1: Of the patients with bleeding concerns, based on our prior experience we anticipate that 44% of the patients randomized to Doxycycline will request additional treatment, and about 80% in the placebo arm. We are purposely overestimating the placebo effect over that noted in our cohort (92% removal requests) to allow for variation in the study group. Given the sample size of 50 per treatment arm, the study will have >90% power to detect the anticipated difference in the need for additional treatment.

Aim 2: Across the two arms, we anticipate that 66 of the 100 patients will request additional treatment and will receive additional treatment with Doxycycline. Within this subset we plan to estimate the method continuation rate following additional treatment. Based on a sample size of 66, the ½ width for a 95% CI around an estimate of 75% is ±10%.

Aim 4: Among the anticipated 66 patients who will request additional treatment for continued unacceptable bleeding at 26 weeks post-ESI insertion, we plan to quantify the patient satisfaction rate. If we assume 75% will be “very satisfied” or “satisfied”, then the ½ width for a 95% CI around this estimate will be ±10%.

5.4.2 Proposed Statistical Analysis:

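### Hypothesis 3.3 claims high continuation and high satisfaction after secondary doxycycline, but its only support rule uses continuation, so the satisfaction half can be called supported whatever the survey shows

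*Combined protocol and SAP*

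**What the plan says.** The combined protocol and SAP deals with satisfaction after secondary treatment in these places:

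- **Section 2.3 (Aim 3)** is worded as estimation of two outcomes: "To determine method continuation and patient satisfaction rate at 26 week post-randomization in patients who choose secondary treatment with Doxycycline".
- **Section 3.3** turns this into a two-part hypothesis: "administration of Doxycycline will result in a high method continuation rate and patient satisfaction rate at 39 weeks post ESI insertion". The next bullet gives the rule: "The above will be supported by method continuation rate of >75% [3, 8] at 26 weeks post-randomization".
- **Section 5.3.1.g** records satisfaction on a 5-point scale, separately for the implant and for bleeding with it. A final survey is given if the implant is removed early.
- **Section 5.3.2** lists satisfaction (item D) and continuation (item E) as distinct endpoints. Item D reads "Patient satisfaction with ESI at 26 weeks post-randomized treatment for patients with continued unacceptable bleeding following primary treatment who receive secondary treatment", and it is to be calculated, with no target.
- **Section 5.4.1** gives precision only. For continuation (labelled Aim 2): "Based on a sample size of 66, the ½ width for a 95% CI around an estimate of 75% is ±10" per cent. For satisfaction (labelled Aim 4): "we plan to quantify the patient satisfaction rate", with 75% in the top two categories assumed in order to show a half-width of 10 points.
- **Section 5.4.2** plans 95% CIs for both outcomes, with no reference value.

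**The concern.** The rule in 3.3 is attached to the whole preceding sentence, which makes two claims, but it tests only one of them. Continuation does not stand in for satisfaction in this protocol, which measures the two with different instruments and lists them as different endpoints. A woman may keep the implant and be dissatisfied with it.

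Section 3.2 shows the contrast. There the satisfaction hypothesis is judged on satisfaction data: "Statistically significant difference in patient satisfaction rates between the placebo and Doxycycline groups will be shown in favor of Doxycycline". In 3.3 the satisfaction claim is judged on continuation data.

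What is at stake is the wording of a conclusion. The report could state that high satisfaction after secondary doxycycline was supported, on a pre-specified rule, when the survey shows otherwise. Settling whether 75% refers to a point estimate or a confidence bound would not cure this, because the satisfaction claim would still not depend on satisfaction.

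**Working it through.** **1. Is there a satisfaction criterion elsewhere for this group?** Sections 5.3.2 D, 5.4.1 and 5.4.2 say that satisfaction will be calculated, quantified and given a CI. None sets a level. The 75% in 5.4.1 is a conditional assumption used to show CI width. The criterion in 3.2 and the expectation in 8.4 compare the randomized arms, whereas everyone in the 3.3 group receives doxycycline unblinded (5.2.1). So no criterion exists.

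**2. Size of the group.** Section 5.4.1 states: "we anticipate that 66 of the 100 patients will request additional treatment and will receive additional treatment with Doxycycline". The Aim 1 rates in the same section give 0.44 × 50 + 0.80 × 50 = 22 + 40 = 62. Both sizes are carried below.

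**3. The plan's own precision figure.** Half-width = 1.96 × √(p(1 − p)/n).

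- n = 66, p = 0.75: 1.96 × √(0.1875/66) = 0.104, which matches the stated 10 points.
- n = 62, p = 0.75: 1.96 × √(0.1875/62) = 0.108.

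**4. What the rule requires.** Read on the point estimate, more than 75% means:

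- n = 62: at least 47 continuing (47/62 = 75.8%; 46/62 = 74.2% fails).
- n = 66: at least 50 continuing (50/66 = 75.8%; 49/66 = 74.2% fails).

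**5. Chance that the rule is met.** Exact binomial tail, P(X ≥ 47 | 62, p) or P(X ≥ 50 | 66, p), where p is true continuation:

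| True continuation | n = 62 | n = 66 |
|---|---|---|
| 70% | 0.20 | 0.19 |
| 75% (planning value, 5.4.1) | 0.51 | 0.51 |
| 80% (assumed) | 0.838 | 0.845 |
| 85% (assumed) | 0.981 | 0.984 |

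The satisfaction rate does not appear in the formula, so each row holds at any level of satisfaction.

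**6. Illustration (assumed counts).** Suppose 50 of 66 women continue, so the rule is met. It is met equally if 7/66 (10.6%), 33/66 (50%) or 50/66 (75.8%) are satisfied. At 33/66 the Wilson 95% CI for satisfaction is 38.3% to 61.7%; at 31/62 it is 37.9% to 62.1%. Both intervals lie below the 75% that 5.4.1 assumes for planning, yet 3.3 as worded would call the hypothesis supported.

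**The case against.** The best case on the other side has four parts.

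- **Satisfaction is estimated on its own data.** This stands. Aim 3 is an estimation aim, satisfaction is a separate endpoint with a planned CI, and women whose implant is removed early are surveyed too. A reader might infer that the trial cannot answer the satisfaction half of Aim 3. The documents do not support that: the estimate will exist and be published, and a contradictory claim beside it would be visible. What remains wrong is the pre-specified statement of what counts as support.
- **The rule does not work in reverse.** This also stands. A reader might infer that continuation of 74% would deny high satisfaction. Section 3.3 says what supports the hypothesis; it does not say that falling short refutes the satisfaction half.
- **It may be loose drafting, with 75% meant for continuation only.** This is plausible, since 5.4.2 contains no success rule for Aim 3. But on that reading the satisfaction half has no criterion at all, and any threshold would be chosen after the data are seen. The same edit is needed.
- **The probabilities measure continuation, not the flaw.** This is fair. They show only how readily the rule could be met. Rates of 80% and 85% are the favourable end; at the plan's own 75% the chance is about one half. The earlier cohort, where 44% of doxycycline-treated women requested removal (1.0 Abstract), suggests about 56% continuing, for which the chance is about 0.001. Those women had a first treatment, so the figure is only indicative.

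**Conclusion.** The point holds, with limited reach. As written, 3.3 lets the satisfaction half of its hypothesis be called supported on continuation data alone, and no other section closes the gap. It affects the conclusion drawn for one single-group, unblinded secondary aim. It does not touch the primary endpoint, the sample size, data collection or any planned estimate.

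The chance of meeting the rule is about 0.51 at 75% true continuation, 0.84 at 80% and 0.98 at 85%, at any level of satisfaction. These figures assume that the rule applies to the point estimate and that 62 to 66 women receive secondary treatment and are all followed. The 80% and 85% rates are assumptions.

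A reader might also infer that the 75% satisfied in 5.4.1 is the missing threshold. The text does not support that: it is a planning assumption for CI width.

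**What to change.** In 3.3, restrict the criterion of more than 75% to the continuation half. Base any statement about satisfaction after secondary treatment only on the satisfaction survey: the proportion in the top two categories for the implant, with its planned 95% CI, including the removal survey for women whose implant is taken out. Report it as an estimate and not as a supported hypothesis.

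If the sponsor wants a satisfaction criterion, pre-specify it separately and state whether the point estimate or a CI bound must meet it. It need not be the 75% in 5.4.1. Requiring both halves to pass would be noticeably stricter: if both true rates were 75% and the outcomes independent (an assumption), the joint chance on point estimates would be about 0.51 × 0.51 = 0.26.

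The cost is one or two sentences in 3.3, with a matching line in 5.4 if a criterion is added. No new data, visits or patients are needed. The downside is that the trial can no longer claim support for the satisfaction half on continuation data alone.

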4.0 Background and Significance

Unintended pregnancy continues to be a major public health issue in the United States. In 2002, nearly half of the 6.4 million pregnancies in the United States were unintended.

Almost half of unintended pregnancies end in elective abortion. [9] Further, 80% of adolescent pregnancies are unintended.[10] The need for a highly effective, safe, estrogen-free, compliance independent and rapidly reversible contraception can be readily met with ESI. The etonogestrel subdermal implant has been available worldwide since 1998 and received United States Food and Drug Administration approval in 2006. Though studies have confirmed its efficacy, convenience, and cost-effectiveness, bleeding irregularities account for up to 43% of requests for early removal. [4, 11] though **the rate of 28.5% was reported in our population.** [29] Other reasons for removal include weight gain, headaches, mood changes and desire for pregnancy, each accounting for about 10-15% of removal requests.[11] Published data regarding bleeding management in US women is limited. A multicenter trial of 330 US women reported a 13 % removal rate for “bleeding pattern changes,” particularly within the first 8 months of use, consistent with international studies. [1, 2]. However, prior trials have excluded women weighing over 130% of ideal body weight [4]. Our retrospective study was the first US study to include women regardless of BMI.[3] Further, an expanded retrospective cohort of 337 women confirmed the efficacy of Doxycycline as 44% of women who received Doxycycline requested removal and 92% of those who received another intervention or declined intervention beyond reassurance requested removal [29]. A recent review of the literature includes interventions for bleeding but admits limited or anecdotal support for these. Further, the first line intervention contains estrogen, which is contraindicated in many ESI users [26]. The intervention in this proposed study is hormone-free.

Rationale for using Doxycycline as initial treatment for ESI related bleeding Doxycycline 100 mg twice daily for 10 days

Matrix metalloproteinases cause endometrial fragility, irregular vessel breakdown, influx of leukocytes, and bleeding. [15, 16] Tetracyclines inhibit matrix metalloproteinase activity independent of their antimicrobial action, with doxycycline being the most potent inhibitor among the tetracyclines [17, 18]. Doxycycline also treats Chlamydia and Ureaplasma infection, which may cause chronic endometritis that presents as abnormal uterine bleeding [19]. A pilot study by Weisberg [21] reported a 50% reduction in ESI-related bleeding duration with doxycycline for 5 days but no long-term improvement and no improvement over placebo in a follow-up study [22]. Doxycycline anti-inflammatory effects are dependent on dose and treatment duration *in vitro* [20] thus supporting a longer therapy course. Clinically there is no precedent for increasing dose beyond 100 mg BID. While there is a clinical precedent for using 10 days of treatment, there is not for 5 days of use. This length of administration was likely used in the Weisberg studies(21,22) for blinding purposes [21,22].In our retrospective cohort (N=9), 10 day course of Doxycycline resulted in bleeding improvement and method continuation in 66% of patients who reported unacceptable bleeding.[3,7] Of 36 untreated patients, 25 (70%) requested early ESI removal.[7]

The published experience with Doxycycline in the treatment of unacceptable bleeding associated with ESI is limited to small, retrospective studies. The validation and subsequent clinical implementation of an evidence-based cost-effective treatment is likely to dramatically increase the acceptability and continuation rates of ESI.

5.0 Experimental Design and Methods

5.1 Overview:

This is a double-blinded, randomized, prospective placebo-controlled clinical trial to be conducted within the Mayo Clinic and the Mayo Clinic Health System.

5.2 Study population

The Mayo Clinic and Mayo Clinic Health System offers a network of collaborative practices throughout the Midwest as well as site in Arizona and Florida. During the past year, 7100 female patients were seen for contraceptive related needs at Mayo Clinic Rochester alone. [26] Electronic medical records are easily accessible for data abstraction and patient followup. Further, the patient population is stable. The loss to followup was only 2% in our 27-month retrospective study. [3] In the Obstetrics and Gynecology department of Mayo Clinic Rochester alone, over 350 ESI devices have been inserted since mid-2007. Over 150 ESI devices were placed in the last year by 12 practitioners and additional practitioners will be trained in November 2011. Additional patients can be readily recruited by Implanon providers from the departments of Family Medicine as well as regional Mayo Clinic Health System sites in Minnesota, such as Albert Lea, Owatonna, Faribault, and Austin, with which close collaborative relationships exist and where over 81,000 women between the ages of 18 and 51 were seen as outpatients in 2009. [25].

5.2.1 Patient selection

After appropriate IRB approval, ESI users aged 18-51 years old who meet the inclusion and exclusion criteria, and sign a written consent will be **enrolled in the study at the time of ESI insertion**. Every effort will be made to insert ESI on the same day as consent unless medically contraindicated. They will complete a prospective symptom diary from date of ESI insertion. All patients will be contacted by study personnel 13 weeks after enrollment and queried as to the presence of unacceptable bleeding. Bleeding concerns will be objectively assessed using a modification of the Pictorial Blood Loss Assessment Chart (PBLAC) [27]. Patient-initiated contact in with bleeding concerns at any time after 13 weeks post ESI insertion will result in enrollment and randomization at the time of contact. **The basis for randomized treatment will be whether or not the bleeding is “unacceptable” to the patient. This is inherently subjective, but constitutes the basis for most removal requests.** Patients who report unacceptable bleeding at 13 weeks post-ESI insertion, and those who call with bleeding concerns after 13 weeks post ESI insertion, will be randomized into two groups (Doxycycline or placebo). Patients who do not report unacceptable bleeding will continue to complete diaries and may be eligible for randomized treatment if unacceptable bleeding develops. Patients will receive diaries sufficient for completion of the study with instructions to contact study personnel if more diaries are needed or if diaries are lost. Patients and investigators will be blinded to the group assignment as well as the study coordinator who will be responsible dispensing of appropriate study medication by the pharmacy.

Patients who continue to have unacceptable bleeding after 4 weeks post-randomized treatment and wish to have secondary treatment will be treated with Doxycycline. Secondary treatment will not be blinded. Rates of unacceptable bleeding and patient satisfaction scores at 26 weeks post-randomized treatment in remaining study participants will be calculated.

[figure not shown]

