- Normal bleeding frequency (3-5 bleeding episodes).
- Frequent bleeding (more than 5 bleeding episodes),
- Prolonged bleeding (1 or more bleeding episodes lasting 14 days or more)

Subgroup analysis may provide additional insight into the efficacy of treatment for various bleeding patterns.

g. Patient satisfaction surveys

Patients will be asked to fill out short satisfaction surveys at randomization measuring satisfaction prior to any treatment, and at 13 and 26 weeks post randomization (see appendix). If patient has their ESI removed prior to 26 weeks post randomization, she will be given a final satisfaction survey at removal. Patient satisfaction surveys will be recorded on a paper formate or via Mayo Clinic website RED Cap.

Patients will rate their satisfaction with a) ESI and b) bleeding with ESI on a 5-point Likert scale ranging from very satisfied to very dissatisfied. If patient has ESI removed prior to 26 weeks post-study enrollment, she will be given a final satisfaction survey at removal.

h. Treatment issues

At enrollment, patients will be provided with a contact number allowing them to reach study personnel at all times with concerns. Instructions will be provided for instances of drug intolerance/allergy, heavy bleeding or other ESI related issues and clinical appointments for evaluation scheduled as needed.

i. Secondary Treatment

If a patient reports unacceptable bleeding at >4 weeks post randomization to treatment or placebo, study participation will be recorded as **need for additional treatment, and will represent the primary endpoint**. If she wishes to have secondary treatment, she will be treated with Doxycycline. Treatment will be limited to two interventions per 13 week

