interval to allow for assessment of efficacy of each course of Doxycycline. Rates of unacceptable bleeding in all patients remaining in the study at 26 weeks post-randomization will be calculated and participation in the study will end. If patients request ESI removal at any time during the study after randomly assigned treatment, study participation will be recorded as a **removal**. Method satisfaction will be assessed at removal and study participation will end. Patients will be provided with alternative contraception of choice at their expense. **Need for additional treatment at >4 weeks post-randomized treatment will represent the primary endpoint.** Satisfaction with ESI at randomization, and 13 and 26 weeks post randomization, and method continuation at 26 weeks post-randomization represent the secondary endpoints.

j. Post-treatment Followup

All patients will be contacted by study personnel at 26 weeks (\pm 2 weeks) post-randomization for final satisfaction survey and weight. Study completion BMI will be calculated. All diaries will be collected for analysis and patients will receive remuneration. When all patients complete the study, the data will be unblinded for analysis.

k. Special Considerations

If patients receive randomized treatment toward the end of the 39 week study interval (rather than at about 13 weeks post ESI insertion), post-treatment data for at least 13 weeks will be collected for a maximum study length of 52 weeks post-ESI insertion.

l. Additional testing

Additional laboratory testing or imaging for heavy or unusual bleeding will be individualized as clinically indicated.

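### The 26-week bleeding rate leaves out women whose implant was removed for bleeding, and the sections disagree on whether early leavers count in 26-week satisfaction

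*Combined protocol and SAP*

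**What the plan says.** **Bleeding.** Section 5.2.1 closes with: "Rates of unacceptable bleeding and patient satisfaction scores at 26 weeks post-randomized treatment in remaining study participants will be calculated". Section 5.3.1.i gives the same limit for bleeding: "Rates of unacceptable bleeding in all patients remaining in the study at 26 weeks post-randomization will be calculated". On removal after randomized treatment, 5.3.1.i adds: "Method satisfaction will be assessed at removal and study participation will end". No section counts a removal for bleeding as unacceptable bleeding at 26 weeks.

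**Satisfaction.** Only section 5.2.1 restricts the 26-week score to remaining women. Section 5.3.2.D defines the endpoint over women who receive secondary doxycycline and says nothing about remaining in the study. Section 5.4.1, in the paragraph labelled Aim 4, bases precision on all 66 women expected to request additional treatment. Exit ratings are planned. Section 2.3 says: "In patients who leave the study prior to 26 weeks post-randomization, patient satisfaction will be recorded at that time". Section 5.3.1.g says that if the implant comes out early, "she will be given a final satisfaction survey at removal". Section 5.4.2 does not say whether these ratings enter the 26-week rate.

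**Removals.** Continuation at 26 weeks (5.3.2.E) and removals for bleeding and for other reasons between weeks 13 and 26 (5.3.2.F) are reported separately.

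**The concern.** Removal is related to the outcome: section 5.2.1 itself describes unacceptable bleeding as the reason behind most removal requests. A bleeding rate among women still in the study therefore sets aside the clearest failures. A reader who took it as the result for everyone treated would think bleeding better controlled than it was.

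For satisfaction the difficulty is ambiguity. An analyst following section 5.2.1 and one following sections 5.3.2.D and 5.4.1 would report different rates from the same data. The choice would be made after the data are in, and satisfaction after secondary treatment is part of Aim 3.

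**Working it through.** **Inputs from the plan**
- Additional treatment requested by 44% on doxycycline and 80% on placebo, 50 women per arm (5.4.1): 0.44 × 50 + 0.80 × 50 = 22 + 40 = 62. Section 5.4.1 states 66. The percentages below are the same for either number.
- Continuation target above 75% (3.3), so at most 25% removed if the target is met.
- Satisfaction of 75% (5.4.1).
- Bleeding accounts for up to 43% of early removal requests among implant users generally (4.0).

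**Assumptions, not in the plan**
- 25% of remaining women have unacceptable bleeding.
- The share *f* of leavers who left for bleeding, and the share *q* of leavers satisfied at exit.
- All leavers are removals; withdrawals without removal would add to them.

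**The plan's own figure.** The 95% half-width is 1.96 × √(0.75 × 0.25 / n). At n = 66 it is 10.4 points, which matches the stated ±10%. With remaining women only, n = 0.75 × 66 = 49.5 and the half-width is 12.1 points. The stated precision therefore goes with the denominator that keeps leavers in.

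**Effect of the denominator.** Of 62 women, 46.5 remain and 15.5 leave.

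Bleeding in all treated women = (0.25 × 46.5 + *f* × 15.5) / 62, against 25% in remaining women:
- *f* = 43%: (11.6 + 6.7) / 62 = 29.5%
- *f* = 50%: (11.6 + 7.75) / 62 = 31%
- *f* = 100%: (11.6 + 15.5) / 62 = 44%

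Satisfaction in all treated women = (0.75 × 46.5 + *q* × 15.5) / 62, against 75% in remaining women:
- *q* = 50%: (34.9 + 7.75) / 62 = 69%
- *q* = one third: (34.9 + 5.2) / 62 = 65%
- *q* = 0: 34.9 / 62 = 56%

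**Range over the share leaving.** If 10% leave, the extremes are 0.90 × 25% + 10% = 32.5% for bleeding and 0.90 × 75% = 67.5% for satisfaction. If 44% leave (the removal-request share with doxycycline in the retrospective cohort, section 1.0), they are 0.56 × 25% + 44% = 58% and 0.56 × 75% = 42%.

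**The case against.** Three objections deserve an answer.

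**Removals are not hidden.** Sections 5.3.2.E and F report continuation and removals by reason. A bleeding rate in current users, shown beside them, is a legitimate description, and 26-week bleeding is not a listed Aim 3 endpoint. This stands as far as it goes, and it limits the harm. It does not make the rate one for all treated women. The removal counts also start at week 13, although secondary treatment can begin after week 4.

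**Satisfaction is not settled.** A reader might infer from section 5.2.1 that the plan discards exit ratings and so overstates satisfaction. The documents do not support that as fact. One sentence points that way, while section 5.3.2.D, the 66-woman basis and the planned exit surveys are all consistent with counting leavers. What is established is a conflict.

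**Bias between arms is conditional.** Section 8.4 expects higher 26-week satisfaction and fewer bleeding removals with doxycycline, so a reader might infer that a remaining-only comparison is biased against doxycycline. That requires removals to differ by arm. After week 4, women in either arm may take open-label doxycycline, and on the plan's rates 40 of 50 placebo women would request additional treatment. This may narrow the difference in removals, and section 8.4 itself allows that it may not reach significance. The Aim 2 hypothesis test is at 13 weeks.

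The 44% and 56% figures are also extremes: they need every leaver to have left for bleeding, or none to be satisfied.

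**Conclusion.** The point holds for bleeding: as written, the 26-week rate drops women removed for bleeding and is too favourable if read as the result for all treated women. For satisfaction it holds as a contradiction between sections that must be resolved before analysis.

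With 25% leaving and 25% bleeding assumed in remaining women, the bleeding rate is understated by about 6 points if half the leavers left for bleeding, and by at most 19. If satisfaction is taken in remaining women only, 75% overstates the all-women rate by about 10 points if a third of leavers are satisfied, and by at most 19. These sizes rest on exit ratings, removal reasons and a bleeding rate that the documents do not give, and they grow or shrink with the share leaving.

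The primary endpoint, need for additional treatment, is not defined on this group and is unaffected.

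**What to change.** In sections 5.2.1 and 5.3.1.i, with a matching sentence in 5.4.2:

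- **Aim 3 denominator:** all women who started secondary treatment.
- **Comparison by arm:** all randomized women whose planned follow-up reaches 26 weeks, defined by time of randomization and not by what happened afterwards. Sections 5.3.1.k and 7.1 guarantee only 13 weeks after late randomization and cap follow-up at 52 weeks from insertion, so a woman randomized after week 26 cannot reach 26 weeks (52 − 26 = 26). Report late-randomized women with shorter planned follow-up separately, and do not count them as failures.
- **Satisfaction:** use the removal or withdrawal survey as the final score.
- **Bleeding:** count removal for bleeding as unacceptable bleeding. Report other removals and withdrawals separately, with a sensitivity range.
- **Supplement:** keep the remaining-only rate, with its denominator shown.

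The cost is analysis wording plus a rule for classifying late-randomized women. Exit surveys and removal reasons are already planned. The reported rates will be somewhat less favourable, and for leavers an exit score will stand in for a 26-week score.
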